6.4.2.3. Maintenance Period LOCF

Maintenance LOCF will be used to handle missing data relative to maintenance supportive estimands for continuous endpoints (Hypothetical). In this analysis, the values subsequent to rescue medication use (per Protocol Section 6.3), treatment discontinuation or transfer to escape arm will be made missing. All missing values will be imputed using LOCF. Baseline value will be used for imputation if there is no postbaseline observation.

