
Other Secondary Endpoints Specific for Maintenance Period:
 
 Percentage of patients from those re-randomized having achieved EASI-75 at Week 16 who continue to exhibit EASI-75 at Week 52 (EASI-75 calculated relative to baseline EASI score) Percentage of patients from those re-randomized having achieved IGA 0 or 1 and a ≥ 2-point improvement from Baseline at Week 16 who continue to exhibit an IGA 0 or 1 and a ≥ 2-point improvement from Baseline at Week 52 Time to loss of EASI-50 in the subset of patients who were re-randomized at Week 16 (EASI-50 calculated relative to baseline EASI score) Time to loss of EASI-75 in the subset of patients who were re-randomized and achieved EASI-75 at Week 16 (EASI-75 calculated relative to baseline EASI score) Time to loss of IGA response, ie, developing an IGA score ≥ 2 with 2 points deterioration of achieved IGA response at Week 16, in the subset of patients who were re-randomized and achieved IGA 0 or 1 and a ≥ 2-point improvement from Baseline at Week 16 	
Major Secondary Endpoints Specific for Maintenance Period:
 
 Percentage of patients from those re-randomized having achieved EASI-75 at Week 16 who continue to exhibit EASI-75 at Week 52 (EASI-75 calculated relative to baseline EASI score) Percentage of patients from those re-randomized having achieved IGA 0 or 1 and a ≥ 2-point improvement from Baseline at Week 16 who continue to exhibit an IGA 0 or 1 and a ≥ 2-point improvement from Baseline at Week 52 Percentage of patients from those with a Pruritus NRS of ≥ 4-points at baseline re-randomized having achieved ≥ 4-point reduction from baseline at Week 16 who continue to exhibit ≥ 4-point reduction from baseline at Week 52 Percentage change in EASI score from Baseline at Week 52 in the subset of patients who were re-randomized at Week 16 
Other Secondary Endpoints Specific for Maintenance Period:
 
 Percentage change in SCORAD (having achieved EASI-75 at Week 16) from baseline at Week 52 Percentage of patients from those with a Pruritus NRS of ≥ 5-points at baseline re-randomized having achieved ≥ 4-point reduction from baseline at Week 16 who continue to exhibit ≥ 4-point reduction from baseline at Week 52 Time to loss of EASI-50 in the subset of patients who were re-randomized at Week 16 (EASI-50 calculated relative to baseline EASI score) Time to loss of EASI-75 in the subset of patients who were re-randomized and achieved EASI-75 at Week 16 (EASI-75 calculated relative to baseline EASI score) Time to loss of IGA response, ie, developing an IGA score ≥ 2 with 2 points deterioration of achieved IGA response at Week 16, in the subset of patients who were re-randomized and achieved IGA 0 or 1 and a ≥ 2-point improvement from Baseline at Week 16

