6.1.3. General Considerations for Analyses During Maintenance Period

Maintenance Period starts at the first injection of study treatment at Week 16 and ends on the date of Week 52 or the ETV (between Weeks 16 and 52) unless specified otherwise.

For the efficacy and health outcome analyses, baseline is defined as the last available value before the first injection in Induction Period and, in most cases, will be the value recorded at Baseline Visit (Day 1).

Unless otherwise specified, efficacy and health outcome scores at Week 16 prior to entering Maintenance Period will be presented for the visit wise reports for Maintenance Period.

Unless specified otherwise, for the safety analyses during Maintenance Period, baseline is defined as the last available value before first injection in Maintenance Period. In most cases, this will be the measure recorded at Week 16. For TEAEs, baseline is the events ongoing just prior to the first injection of the study drug injection at Week 16.

For patients in the Modified Maintenance Primary Population, Modified Maintenance Secondary Population, Maintenance Primary Population, and Maintenance Secondary Population who met escape criteria (EASI-50 nonresponse) and escaped to lebrikizumab 250 mg Q2W at Weeks 24, 32, 40 and 48, only data in the Maintenance Blinded Period (up to the time of escape) will be included in both efficacy and safety analyses.

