6.2.2.1. Maintenance Primary Estimand (Hybrid)

The maintenance primary estimand is a hybrid estimand representing the clinical question of interest: what is the difference between treatment conditions, ie, Lebrikizumab vs Placebo, in the target patient population, in successful responses or means after 52 weeks achieved without use of systemic rescue medication, without transferring to escape arm, if topical rescue medication were not available and if all patients continued with treatment except those who discontinued due to lack of efficacy?

The maintenance primary estimand is described by the following attributes:

- Population: Modified Maintenance Primary Population as described in Section 6.1.1.
- Endpoint: apply to all major and other secondary endpoints for Maintenance Period
- How to account for intercurrent events (ICEs)
 - Subjects who require any use of systemic rescue medication, discontinue treatment due to lack of efficacy after week 16, or transfer to escape arm will be

considered as treatment failures, ie, non-responder, after the ICEs. Therefore, composite strategy is used for these types of ICEs.

- b. For subjects who require any use of topical rescue medication, a hypothetical strategy will be used to estimate what the treatment effect would have been if subjects continued with treatment. Therefore, hypothetical strategy is used for these types of ICEs.
- c. For subjects who discontinue treatment due to reasons other than lack of efficacy after week 16, a hypothetical strategy will be used to estimate what the treatment effect would have been if subjects continued with treatment. Therefore, hypothetical strategy is used for these types of ICEs.

D. Population-level summary: difference in response proportions or means between treatment conditions

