6.2.2.4. Maintenance Supportive Estimand for Continuous Endpoints (Hypothetical)

The maintenance supportive estimand for continuous endpoints only is a hypothetical estimand representing the clinical question of interest: what is the difference between treatment conditions, ie, Lebrikizumab vs Placebo, in the target patient population, in means after 52 weeks if rescue medication was not available and all patients adhered to the treatment and did not transfer to escape arm?

The maintenance supportive estimand for continuous endpoints is described by the following attributes:

- A. Population: Modified Maintenance Primary Population as described in Section 6.1.1.
- B. Endpoint: apply to all major and other secondary continuous endpoints for Maintenance Period
- C. How to account for intercurrent events (ICEs)
 - a. For subjects who require any use of rescue medication, discontinue treatment after week 16, or transfer to escape arm, a hypothetical strategy will be used to estimate what the treatment effect would have been if rescue medication was not available and all subjects adhered to the treatment and did not transfer to escape arm. Therefore, hypothetical strategy is used for these types of ICEs.

D. Population-level summary: difference in means between treatment conditions

Analytical details on how missing data including those as a result of intercurrent events will be handled for Maintenance Period can be found in Section 6.4.2. Detailed analyses relative to estimands including analysis type, method and imputation, population, time point, and treatment comparisons for efficacy/health outcomes analyses can be found in Section 6.11.

The following table (Table KGAC.6.4) summarizes the analytical strategies that will be conducted on the intercurrent events for the four maintenance estimands.

Table KGAC.6.4. Analysis of Primary and Supportive Estimands for Maintenance Period

Maintenance Estimand	Analysis Strategy for Intercurrent Events				Transfer to escape arm	Missing Data Imputation Method		
	Rescue Medication		Treatment Discontinuation					
	Topical rescue medication	Systemic rescue medication	Due to lack of efficacy	Due to any other reasons				
Maintenance Primary Estimand (Hybrid)	Hypothetical: Set to missing	Composite: Set to baseline	Composite: Set to baseline	Hypothetical: Set to missing	Composite: Set to baseline	MCMC-MI		

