6.4.2. Handling of Dropouts or Missing Data for Maintenance Period

For maintenance efficacy analysis relative to the maintenance primary estimand, the method of handling missing data including those as a result of intercurrent events will be Markov Chain Monte Carlo Multiple Imputation (MCMC-MI). The description of maintenance MCMC-MI method can be found in Section 6.4.2.1.

MCMC-MI will also be used to handle missing data relative to the maintenance supportive estimand (Hybrid) as described in Section 6.4.2.1.

For efficacy analysis relative to the maintenance supportive estimand for categorical endpoints (Composite), missing data including those as a result of intercurrent events will be imputed as non-responder. The description of maintenance non-responder imputation (NRI) can be found in Section 6.4.2.2.

For efficacy analysis relative to the maintenance supportive estimand for continuous endpoints (Hypothetical), missing data including those as a result of intercurrent events will be imputed using Last Observation Carried Forward (LOCF). The description of maintenance LOCF can be found in Section 6.4.2.3.

Table KGAC.6.9 describes the planned imputation methods for efficacy and health outcome endpoints for Maintenance Period.

Table KGAC.6.9. Imputation Techniques for Various Variables During Maintenance Period

Type of Endpoints	Efficacy and Health Outcome Endpoints	Estimand (Analysis strategy for Intercurrent Events)	Missing Data Imputation Method (Analysis Method)
Categorical	IGA, EASI, and Pruritus NRS related categorical endpoints at pre-specified timepoints	Maintenance Primary Estimand (Hybrid)	MCMC-MI (CMH)
		Maintenance Supportive Estimand (Hybrid)	MCMC-MI (CMH)
		Maintenance Supportive Estimand (Composite)	NRI (CMH)
	Remaining categorical endpoints	Maintenance Supportive Estimand (Composite)	NRI (CMH)
Continuous	EASI percent change, Pruritus NRS percent change	Maintenance Primary Estimand (Hybrid)	MCMC-MI (ANCOVA)
		Maintenance Supportive Estimand (Hybrid)	MCMC-MI (ANCOVA)
		Maintenance Supportive Estimand (Hypothetical)	LOCF (ANCOVA)
	Remaining continuous endpoints	Maintenance Supportive Estimand (Hypothetical)	LOCF (ANCOVA)

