6.4.2.2. Maintenance Period NRI

The nonresponder imputation (NRI) method will be used to handle missing data relative to the maintenance supportive estimand for categorical endpoints (composite). Patients who receive rescue medication (per Protocol Section 6.3), discontinue treatment, or transfer to escape arm will be set to non-response subsequent to this time through Week 52 Intermittent missing values will also be set to non-response.

Re-randomized patients without at least 1 postbaseline observation will also be defined as nonresponders for all visits for the NRI analysis.

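### After escape or rescue, maintenance LOCF ordinarily enters the pre-maintenance Week 16 score as the Week 52 value of continuous SCORAD, EQ-5D, PROMIS and ACQ-5; for SCORAD percentage change this also conflicts with SAP 6.2.2.1

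*SAP*

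**What the plan says.** SAP 6.4.2.3 describes the LOCF analysis for continuous maintenance endpoints: "the values subsequent to rescue medication use (per Protocol Section 6.3), treatment discontinuation or transfer to escape arm will be made missing". Missing values are then filled by LOCF, with the fallback "Baseline value will be used for imputation if there is no postbaseline observation". The section does not name the visit whose value is carried. It also does not say whether an early-termination (ET) value counts as coming after discontinuation.

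For maintenance efficacy analyses, SAP 6.1.3 says "baseline is defined as the last available value before the first injection in Induction Period".

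The target of the LOCF analysis is set in 6.2.2.4. It is the Week 52 mean had rescue been unavailable and "all patients adhered to the treatment and did not transfer to escape arm".

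SAP 6.2.2.1 defines a different, primary estimand for maintenance, and its stated scope is "apply to all major and other secondary endpoints for Maintenance Period". There, escape, systemic rescue and discontinuation for lack of efficacy are failures. Table KGAC.6.4 implements this by setting values to baseline, with MCMC-MI for the rest.

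Table KGAC.6.9 gives EASI and Pruritus NRS percent change both hybrid estimands plus LOCF. "Remaining continuous endpoints" get only LOCF with ANCOVA. Table KGAC.6.12 follows this for continuous SCORAD, EQ-5D, PROMIS and ACQ-5 in the Modified Maintenance Primary Population. One of these is a named maintenance endpoint in Table KGAC.4.1 (EMA, other secondary): "Percentage change in SCORAD (having achieved EASI-75 at Week 16) from baseline at Week 52".

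**The concern.** LOCF is usually defended on the ground that the last value was taken shortly before the patient left. Here it was taken before the randomized maintenance comparison started. Every re-randomized patient was a responder at Week 16, so the carried score says nothing about the assigned maintenance regimen. For a patient who has just lost EASI-50 it assumes that the response was fully kept. That is not a credible estimate of the 6.2.2.4 target, especially for a placebo patient who has relapsed.

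Arm means would look too favourable. If escape is more frequent on placebo, the part of the treatment difference that comes from escape would disappear. For SCORAD percentage change the SAP also promises a primary-estimand analysis that its own tables do not contain.

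**Working it through.** The SAP states no figure here to reproduce. The check sets the visit schedule against the imputation rule, then the endpoint list against the analysis tables, and then gives an illustration.

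**Step 1: which value is carried.** Escape occurs at Week 24, 32, 40 or 48 (SAP 5.1.3.2). From Protocol 7.10 to 7.19 and Appendix 1, the last scheduled score at or before escape is:

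| Scale | Wk 24 | Wk 32 | Wk 40 | Wk 48 |
|---|---|---|---|---|
| SCORAD, EQ-5D, PROMIS, ACQ-5 | 16 | 16 | 16 | 16 |
| DLQI/CDLQI | 16 | 32 | 32 | 32 |
| EASI | 24 | 32 | 40 | 48 |

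The exacerbation visit (Protocol 7.22) adds only IGA, BSA and EASI. An extra unscheduled SCORAD could be carried, but none is planned. Topical rescue, permitted in maintenance by Protocol 6.3, triggers the same deletion. Step 1 needs no assumption about escape rates.

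**Step 2: other tests of the same scales.** SCORAD75/90 and the EQ-5D no-problem items have NRI tests and are unaffected. PROMIS and ACQ-5 have none, so LOCF is their only maintenance test.

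**Step 3: conflict with 6.2.2.1, scale by scale.**
- SCORAD percentage change at Week 52 is listed under the maintenance heading of Table KGAC.4.1. The conflict is direct.
- EQ-5D, PROMIS and DLQI/CDLQI appear only in the general list of by-visit endpoints. The conflict depends on reading those as maintenance endpoints.
- ACQ-5 is listed only to Week 16. No maintenance endpoint is listed, although Table KGAC.6.12 plans a maintenance test.

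For topical rescue both approaches set values to missing, so they differ only in MCMC-MI against LOCF. For escape and systemic rescue the strategy itself differs.

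**Step 4: illustration.** The assumptions, none of them from the documents, are: SCORAD change of −75% at Week 16, held by active non-escapees; placebo non-escapees worse by d points at Week 52; active escape eA = 15%; placebo escape eP varied.

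- Week 16 carried: difference = (1 − eP) × d
- Escapees set to baseline, as in 6.2.2.1: difference = 75 × (eP − eA) + (1 − eP) × d

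| eP | Wk 16 carried, d=0 | Wk 16 carried, d=10 | Set to baseline, d=0 | Set to baseline, d=10 |
|---|---|---|---|---|
| 15% | 0 | 8.5 | 0 | 8.5 |
| 25% | 0 | 7.5 | 7.5 | 15.0 |
| 40% | 0 | 6.0 | 18.75 | 24.75 |
| 50% | 0 | 5.0 | 26.25 | 31.25 |

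At 40% and d=0, 75 × 0.25 = 18.75. This scales with the assumed Week 16 level: 50 × 0.25 = 12.5 at −50%, and 90 × 0.25 = 22.5 at −90%. With Week 16 carried and d=0, each arm's mean stays at −75 whatever its escape rate.

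**Step 5: power cost of the composite analysis.** Planning figures give 400 × 2/3 × 0.48 = 128 lebrikizumab responders, split 2:2:1 as 51/51/26. The simulation compared 51 with 26 patients using ANCOVA on treatment, baseline SCORAD and region (SD 12 for baseline, Week 16 change and later drift). Rejection rates were:

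| eP, d | Week 16 LOCF | Set to baseline |
|---|---|---|
| 15%, 10 | about 55% | about 20% |
| 15%, 15 | about 87% | about 42% |
| 40%, 10 | about 32% | about 86% |

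**The case against.** **The scope wording in 6.2.2.1 may simply be loose.** The time-to-loss endpoints sit under the same maintenance heading, yet Table KGAC.6.12 gives them no estimand, so the word all is not applied literally. This has force for EQ-5D, PROMIS, DLQI/CDLQI and ACQ-5, where narrowing one sentence would settle the matter. It does not dispose of SCORAD percentage change. That is a continuous Week 52 endpoint of the same kind as EASI percent change, which does receive the primary estimand.

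**A reader might infer that the carried value is genuinely open between Week 16 and Day 1**, because 6.4.2.2 says "Re-randomized patients without at least 1 postbaseline observation will also be defined as nonresponders for all visits for the NRI analysis" and escaped patients contribute only blinded-period data. The documents support this only weakly. By 6.1.3 baseline is pre-induction, so Week 16 is postbaseline. The fallback still has a use, because a patient re-randomized on IGA or EASI may lack a Week 16 questionnaire. One clarifying line is warranted, not a claim that the result could be either 0 or 18.75.

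**A reader might infer that LOCF is unbiased when escape rates are equal.** It is not, because topical rescue also triggers deletion. At 15% escape in each arm, d=10 and topical rescue in 20% of placebo non-escapees, the difference is 0.85 × 0.8 × 10 = 6.8, against 8.5 without that deletion.

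**The point differences compare two estimands.** This stands. Bias against the 6.2.2.4 target is not calculated, and the documents give nothing from which to calculate it.

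**Setting every scale to baseline is debatable.** This stands, above all for ACQ-5: escape is defined by skin response, and nothing in the documents ties it to asthma control.

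**Conclusion.** The point holds in a limited form. From the visit schedule alone, maintenance LOCF ordinarily uses a pre-maintenance responder score as the Week 52 value of continuous SCORAD, EQ-5D, PROMIS and ACQ-5 after escape or rescue. It is the only inferential maintenance analysis of those continuous scores. The conflict with 6.2.2.1 is firm for SCORAD percentage change, arguable for EQ-5D, PROMIS and DLQI/CDLQI, and absent as a listed endpoint for ACQ-5.

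The size cannot be stated from the documents. The figures above illustrate assumed escape rates and SCORAD levels. They show that the two analyses can diverge widely when escape is unequal, with no fixed direction for power.

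It would be wrong to infer that the trial's main maintenance conclusions are compromised. These are other secondary endpoints outside multiplicity control. Relapse remains visible in escape counts (SAP 6.7), time to loss of EASI-50, EASI-75 and IGA response, and Week 52 EASI percent change under the primary estimand.

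**What to change.** 1. In Tables KGAC.6.9 and KGAC.6.12, analyse Week 52 SCORAD percentage change under the Maintenance Primary Estimand as already defined. Label it a composite strategy, and make LOCF supplementary. Add a SCORAD seed to Table KGAC.6.10, which now lists only IGA, EASI and Pruritus NRS.
2. For EQ-5D, PROMIS, DLQI/CDLQI and ACQ-5, either do the same or narrow the scope sentence in 6.2.2.1. Set-to-baseline should not be required for ACQ-5. In either case, do not present the LOCF comparison as evidence of maintained response.
3. In 6.4.2.3, state that Week 16 is carried when no later score exists, consistent with 6.1.3, and whether an ET value counts as subsequent to discontinuation.

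The cost is SAP wording, a seed and some programming, with no new data. If maintenance treatment has already been unblinded, the added analysis should be labelled post hoc.

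The composite analysis has real downsides. It answers a different question and loses power when escape rates are similar (Step 5). It can also overstate the loss: if SCORAD at escape were still 25% better than baseline, the 40% against 15% case at d=0 would give 50 × 0.25 = 12.5 points rather than 18.75.

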6.5. Multicenter Studies

This study will be conducted by multiple investigators at multiple sites internationally. Typically, a logistic regression with treatment, site, and treatment-by-site may be used to assess the consistence of treatment effect in sites. However, due to a large number of sites and countries and relative small sample size in the study, this logistic regression model will not likely converge. The site will not be adjusted as a covariate. Instead, the subgroup analysis on the region will be evaluated. The countries will be categorized into geographic regions as in Section [6.3](#). Subgroup analysis details are provided in Section [6.15.1](#).

For the analysis of the primary endpoint, the presence of a treatment-by-geographic region interaction will be tested at 10% significance level. Treatment group comparisons for the primary endpoint will be presented separately for each geographic region. When there is evidence of an interaction ($p < .10$), descriptive statistics may be used to assess whether the interaction is quantitative (ie, the treatment effect is consistent in direction but not size of effect) or qualitative (the treatment is beneficial for some but not other geographic regions or countries).

6.6. Multiple Comparisons/Multiplicity

6.6.1. Multiplicity Control for FDA

A prespecified graphical multiple testing approach (Bretz et al. 2009, 2011) will be implemented to control the overall Type I error rate at two-sided alpha of 0.05, for all primary and major secondary endpoints for FDA. Multiple testing adjusted p-values using “Algorithm 2” described by Bretz et al. (2009) will be calculated, and any hypothesis tests with a multiple testing adjusted p-value of less than 0.05 will be considered statistically significant. This graphical approach is a closed testing procedure; hence, it strongly controls the family-wise error rate across all endpoints (Bretz et al. 2009, 2011; Alesh et al. 2014). Each hypothesis is represented as a node in a graph. Directed arrows between the nodes with associated weights represent how alpha is passed from its initial allocation to other nodes.

The following is a list of primary and major secondary endpoints to be tested for FDA.

Primary endpoint:

- [IGA01 W16] Percentage of patients with an Investigator Global Assessment (IGA) score of 0 or 1 and a reduction ≥ 2 points from Baseline to Week 16.

Major secondary endpoints:

- [EASI-75 W16] Percentage of patients achieving EASI-75 ($\geq 75\%$ reduction from Baseline in Eczema Area and Severity Index [EASI] score) at Week 16.
- [EASI-90 W16] Percentage of patients achieving EASI-90 ($\geq 90\%$ reduction from Baseline in EASI score) at Week 16.
- [Pruritus NRS-4 W16] Percentage of patients with a Pruritus Numerical Rating Scale (NRS) of ≥ 4 -points at Baseline who achieve a ≥ 4 -point reduction from Baseline to Week 16.
- [Pruritus NRS-4 W4] Percentage of patients with a Pruritus NRS of ≥ 4 -points at Baseline who achieve a ≥ 4 -point reduction from Baseline to Week 4.
- [Pruritus NRS-4 W2] Percentage of patients with a Pruritus NRS of ≥ 4 -points at Baseline who achieve a ≥ 4 -point reduction from Baseline to Week 2.
- [IGA01 W4] Percentage of patients with an IGA score of 0 or 1 and a reduction ≥ 2 points at Week 4.
- [IGA01 Adult W16] Percentage of patients with an IGA score of 0 or 1 and a reduction ≥ 2 points at Week 16 in adults.

- [Sleep loss W16] Percentage of patients with a Sleep-loss score ≥ 2 points at Baseline who achieve a ≥ 2 points reduction from Baseline at Week 16.

Figure KGAC.6.2 describes the graphical testing scheme for FDA.

[figure not shown]

Figure KGAC.6.2. Graphical approach to control type 1 error rate for Study J2T-DM-KGAC for FDA purposes.

